8.4.2 Safety Endpoints

Safety measurements are described in Section 7.

8.5 Analysis Population

8.5.1 Efficacy Analysis Population

The analysis of primary efficacy endpoints are based on the All Subjects as Treated (ASaT) population, ie, subjects will be included if they receive at least one dose of study medication.

Supportive analyses will be conducted in the Full Analysis Set (FAS) population, which consists of all subjects who 1) receive at least one dose of study medication; 2) have a

baseline disease assessment, and 3) have a post baseline disease assessment OR discontinue the trial due to progressive disease/drug related AE.

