observed were Grade 1 and 2, which resolved with appropriate clinical management. No Grade 4-5 drug related adverse events (DRAEs) were reported, but two patients discontinued therapy due to a DRAE: Grade 2 pneumonitis, and Grade 3 nephrotic syndrome [47]. The present study, KEYNOTE-087 (ClinicalTrials.gov, NCT02453594), is a multicenter, single-arm, multicohort phase 2 study of pembrolizumab in 3 cohorts of patients. Among 210 treated patients in cohorts 1 (n = 69), 2 (n = 81), and 3 (n = 60), all patients had refractory disease or relapsed HL. Per blinded independent central review, the ORR was 69.0% (95% CI, 62.3% to 75.2%), and the CRR was 22.4% (95% CI, 16.9% to 28.6%). By cohort, ORRs were 73.9% for cohort 1, 64.2% for cohort 2, and 70.0% for cohort 3. Thirty-one patients had a response \geq 6 months. With a median of 13 treatment cycles, the most common treatment-related AEs (TRAEs) were hypothyroidism (12.4%) and pyrexia (10.5%). The most common grade 3/4 TRAEs were neutropenia (2.4%), dyspnea (1%), and diarrhea (1%). Immune-mediated AEs (events with potentially drug-related immunologic causes regardless of treatment attribution) and infusion-related reactions were reported in 60 patients (28.6%), most commonly hypothyroidism (13.8%). Nine patients (4.3%) discontinued because of TRAEs (myocarditis, myelitis, myositis, pneumonitis, infusion-related reactions, cytokine release syndrome), and 26 patients (12.4%) experienced TRAEs resulting in treatment interruptions. Two patients died during follow-up as a result of septic shock and acute graft-versus-host disease, respectively; neither of these deaths were considered to be treatment related [48]. Taken together, the observed efficacy and safety data indicate that MK-3475 has the potential to alter the disease course in these RRHL patients and potentially prolong patient survival.

In conclusion, pembrolizumab demonstrates a very promising anti-cancer activity in relapsed or refractory Hodgkin Lymphoma patients with an acceptable safety profile compared to those of existing therapeutic options. On-going and planned studies will allow for a more comprehensive analysis of benefit/risk balance of pembrolizumab.

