Full Physical Examination ⁱ	X				X					X ⁱ	X ⁱ		
Directed Physical Examination ⁱ			X				X						
Vital Signs and Weight ^j	X	X	X	X	X	X	X	X	X				
ECOG Performance Status	X	X	X	X	X	X	X	X	X				
Neck, Chest, Abdominal, Pelvic PET/CT ^k					X ^{l,k}				X ^k	X ^m		X ^b	
Disease Response Assessment by Cheson Criteria 2007 ^k	X				X				X ^k	X			X
Assessment of Lymphoma B Symptoms ^k					X				X ^k	X			X
Laboratory Procedures/Assessments: analysis performed by local laboratory													
Pregnancy Test – Urine or Serum β-HCG ⁿ	X												
CBC with Differential ^o	X	X	X	X	X	X	X	X ^q	X	X ^p			
Comprehensive Chemistry Panel ^o	X	X	X	X	X	X	X	X ^q	X	X ^p			
LDH ^o					X				X ^r	X	X ^p		
Urinalysis ^o	X	X		X		X		X ^s		X ^p			
T3 (or FT3 per local standard), FT4 and TSH ^o	X	X		X		X		X ^s	X	X ^p			

Trial Period:	Treatment Cycles ^a									End of Treatment	Post-treatment		
	1	2	3	4	5	6	7	8	9		Post-Treatment Safety Follow-up	Follow-up Visits ^b	Survival Follow-up ^c
Treatment Cycle/Title:					To be repeated beyond 9 cycles								
Scheduling Window (Days) ^d	+ 3	± 3	± 3	± 3	± 3	± 3	± 3	± 3	± 3	At time of Discon	30 days post Last Infusion (±3 days)	Every 12 weeks (±7 days)	Every 12 weeks (±14 days)
Bone Marrow Biopsy & Aspirate ^{t, u}	X												
Lymphoma adequate organ function laboratory tests ^v	X												

- a. IV pembrolizumab at 200mg flat dose over 30 minutes will be administered once every 3 weeks. In general, assessments/procedures are to be performed on Day 1 and prior to the first dose of treatment for each cycle unless otherwise specified.
- b. In subjects who discontinue study therapy without documented disease progression, every effort should be made to continue monitoring their disease status by radiologic imaging every 12 weeks (± 7 days) until (1) the start of new anti-cancer treatment, (2) documented disease progression, (3) death, or (4) the end of the study, whichever occurs first. The imaging schedule should proceed every 12 weeks from the day of the last imaging performed before subject enters the follow up period.

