7.1.2.6.4 Timing of Disease Assessments

Uniform disease response assessments will occur every 12 weeks following the first assessment at Week 12 (see [Table 6](#) below).

Table 6 Disease Response Assessments

Indication	Assessment Frequency
HL (Cohorts 1, 2, and 3)	Every 12 weeks following first assessment at Week 12

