7.1.4 Other Procedures

7.1.4.1 Withdrawal/Discontinuation

Subjects who discontinue/withdraw from treatment prior to completion of the treatment regimen should be encouraged to continue to be followed for all remaining study visits.

When a subject discontinues/withdraws from participation in the trial, all applicable activities scheduled for the final trial visit should be performed at the time of discontinuation. Any adverse events which are present at the time of discontinuation/withdrawal should be followed in accordance with the safety requirements outlined in Section 7.2 - Assessing and Recording Adverse Events. Subjects who attain a CR may discontinue treatment with the option of restarting treatment if they meet the criteria specified in Section 7.1.5.2.2. After discontinuing treatment following assessment of CR, these subjects should return to the site for a Safety Follow-up Visit (described in Section 7.1.5.3.1) and then proceed to the Follow-Up Period of the study (described in Section 7.1.5.4).

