8.3 Hypotheses/Estimation

Objectives and hypotheses of the study are stated in Section 3.

Unless stated otherwise, objectives will be evaluated within each Cohort. There is one hypothesis, within each Cohort, to be formally tested in this study, ie, whether the ORR is greater than a fixed control rate using the IWG criteria based on independent central review; details on how this will be tested appear below in Section 8.6.1.1. Secondary objectives,

again within each Cohort, will not involve hypothesis testing, and will assess the efficacy of pembrolizumab on secondary efficacy endpoints (CRR, PFS, DOR, and OS) and will include, where appropriate, assessments based on investigator and Lugano classification; details appear below in the corresponding sections of Section 8.6.1.

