8.4.1 Efficacy Endpoints

Efficacy endpoints that will be evaluated are listed below, followed by the descriptions of the derivations of selected endpoints.

The primary efficacy endpoint is the Overall Response Rate (ORR), defined as the proportion of subjects in the analysis population who have complete remission (CR) or partial remission (PR) using IWG criteria (Cheson 2007) at any time during the study. Response for the primary analysis will be determined by central review.

Secondary efficacy endpoints include: (1) ORR according to investigator (site) assessment using IWG criteria; (2) ORR according to central review using Lugano 5-point classification; (3) complete remission rate (CRR), defined as the proportion of subjects in the analysis population who have complete remission (CR) by IWG criteria; (4) progression-free survival (PFS), defined as the time from first dose to the first documented disease progression according to IWG criteria or death due to any cause, whichever occurs first; (5) duration of response (DOR), defined as time from first IWG response to disease progression in subjects who achieve a PR or better, and (6) overall survival (OS), defined as time from first dose to date of death.

Exploratory efficacy endpoints include: (1) eligibility for SCT post-study therapy (yes/no); (2) receiving SCT following post-study therapy (yes/no); (3) ORR, (4) DOR, (5) CRR, and (6) PFS, incorporating response assessments for subjects continuing pembrolizumab treatment after initial progression.

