8.6.1.5 Overall Survival (OS)

The median overall survival, if reached, will be estimated in the given analysis population, separately by cohort. In addition, the Kaplan-Meier method will be used to estimate the survival curve, separately by Cohort.

Table 13 Efficacy Analysis Methods for Primary and Secondary Efficacy Endpoints

Endpoint/Variable	Statistical Method	Analysis Population	Missing Data Approach
Primary:			
Overall Response Rate 
 • IWG criteria (2007) 
 ◦ Central review 	Exact test of binomial parameter; 2-sided 95% exact CI	ASaT/FAS	Subjects with missing data are considered non-responders
Secondary:			
Overall Response Rate 
 • IWG criteria (2007) 
 ◦ Study site • Lugano criteria (2014) 
 ◦ Central review 	Point estimate; 2-sided 95% exact CI	ASaT/FAS	Subjects with missing data are considered non-responders
Complete Remission Rate 
 • IWG criteria (2007) 
 ◦ Central review ◦ Study site • Lugano criteria (2014) 
 ◦ Central review 	Point estimate; 2-sided 95% exact CI	ASaT/FAS	Subjects with missing data are considered non-responders
Progression-free survival 
 • IWG criteria (2007) 
 ◦ Central review ◦ Study site 	Summary statistics using Kaplan-Meier method	ASaT/FAS	Censored at last assessment (see Table 12 for sensitivity analyses based on alternative censoring)
Duration of Response 
 • IWG criteria (2007) 
 ◦ Central review ◦ Study site 	Summary statistics using Kaplan-Meier method	All responders	Non-responders are excluded in analysis
Overall survival	Summary statistics using Kaplan-Meier method	ASaT/FAS	Censored at last assessment

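### The FAS has no entry route for a treated subject who dies of another cause before any post-baseline assessment, yet Table 13 plans supportive PFS and OS in the FAS

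*Combined protocol and SAP*

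**What the plan says.** Section 8.5.1 bases the primary efficacy analysis on ASaT, which needs only one dose of study medication. It reserves the FAS for supportive analyses. The FAS needs one dose, a baseline disease assessment and, as criterion 3, that subjects "have a post baseline disease assessment OR discontinue the trial due to progressive disease/drug related AE". Death is not listed as a route.

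Table 13 (at the end of 8.6.1.5) gives ASaT/FAS as the population for PFS and OS, both by Kaplan-Meier. Section 8.4.1 counts death from any cause as a PFS event and has "overall survival (OS), defined as time from first dose to date of death". Table 6 in 7.1.2.6.4 sets disease assessments as "Every 12 weeks following first assessment at Week 12". Footnote m of the 6.1 flow chart allows an earlier first assessment if the investigator judges that the patient is clinically progressing.

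For ORR and CRR, the missing-data rule in Table 13 is "Subjects with missing data are considered non-responders".

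**The concern.** FAS membership depends on what happens after the first dose, and for PFS and OS one way of failing to qualify is the endpoint event itself. Suppose a treated subject dies of an unrelated infection in Week 6 without a scan. That subject has no post-baseline assessment and did not discontinue for progression or a drug-related AE. The death counts in the ASaT curves, while the subject is missing from the FAS curves.

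A supportive analysis should show whether the main result is robust. Here, part of any agreement or improvement in the FAS could come from who was left out. Section 8.6.1 repeats all Table 13 endpoints at Week 24, one year, two years and yearly after that, so the omission would recur in each update that reports the FAS.

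A related gap affects ORR and CRR. Table 13 scores missing data as non-response, but some subjects with no assessment have already left the FAS denominator.

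**Working it through.** **The plan's own figure.** No stated figure rests on the FAS. Section 8.8 sets 60 subjects per cohort in ASaT, with at least 93% power at one-sided 2.5% for 40% against 20%. The exact binomial reproduces this: 19 or more responses of 60 has alpha 0.0221 and power 0.928, or 0.922 with the 6/30 futility rule (the plan says approximately 92%). The lower cut-off printed in 8.8 is a separate matter. FAS membership enters none of these figures.

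**Membership check.** Take a treated subject with a baseline assessment who dies of another cause before any post-baseline assessment.

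- Post-baseline assessment: none.
- Discontinued for progressive disease: no.
- Discontinued for a drug-related AE: no.
- Result: in ASaT as a PFS and OS event, and not in the FAS.

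**Size.** Inputs are N = 60 per cohort (8.8) and k omitted deaths. The documents do not give k, so I assume 1 or 2. I also assume no censoring and an ASaT survival S between 50% and 95% at a later time t.

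If m subjects are event-free at t, after the last omitted death, then S_ASaT(t) = m/N and S_FAS(t) = m/(N - k). Hence S_FAS(t) = S_ASaT(t) × N/(N - k).

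Week 12, if there are no other early events:

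- k = 1: ASaT 59/60 = 98.3%; FAS 59/59 = 100%.
- k = 2: ASaT 58/60 = 96.7%; FAS 58/58 = 100%.

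Later times:

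- k = 1, factor 60/59 = 1.0169: 50% becomes 50.8%, and 95% becomes 96.6%. The excess is 0.8 to 1.6 points.
- k = 2, factor 60/58 = 1.0345: 50% becomes 51.7%, and 95% becomes 98.3%. The excess is 1.7 to 3.3 points.

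**Direction before the omitted death.** The excess starts only at that death. Suppose five subjects who are in the FAS have PFS events before Week 8, and the omitted death comes at Week 11. At Week 8, ASaT is 55/60 = 91.7% and FAS is 54/59 = 91.5%, so the FAS is marginally lower. After Week 11, ASaT is 54/60 = 90.0% and FAS stays at 54/59 = 91.5%, which is the factor 60/59 again.

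**Response rates.** With an illustrative 24 responders, 24/60 = 40.0% becomes 24/59 = 40.7% or 24/58 = 41.4%.

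**The case against.** The strongest reply is that nothing the plan relies on is affected. Table 11 names ASaT for efficacy, 8.5.1 calls FAS analyses supportive, and 8.3 says that secondary objectives "will not involve hypothesis testing". Every PFS and OS output is also planned in ASaT, so a reader can compare the two. This stands, and it is why the point is minor. It does not justify a supportive survival curve that leaves out some of its own events.

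A second reply is that 8.6.1.3 always treats death as a progression event. That rule governs how PFS events are counted and dated. It does not turn such a death into discontinuation for progressive disease under 8.5.1, and it does not reach OS.

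Three stronger readings are tempting, and the documents do not support them.

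- *Everyone who leaves before Week 12 drops out of the FAS.* The flow charts in 6.1 and 6.2 carry a row for "Disease Response Assessment by Cheson Criteria 2007" that includes the discontinuation visit, and 7.1.4.1 says that "all applicable activities scheduled for the final trial visit should be performed at the time of discontinuation". Many subjects who stop early and alive could therefore qualify. Those still excluded are other-cause early deaths, plus subjects lost to follow-up or missing that assessment without having stopped for progression or a drug-related AE. Excluding subjects who are alive could move FAS OS either way.
- *The two deaths reported in 4.3 are examples.* The text says "neither of these deaths were considered to be treatment related", but it places them during follow-up and gives no timing. One was from acute graft-versus-host disease. Section 5.1.3 excludes recent allogeneic transplant and, after an older one, any symptoms of that disease. That death more plausibly followed a transplant after study treatment, which 8.6.3.4 describes for responders, who by definition have been assessed.
- *The omission can only raise the FAS curve.* The Week 8 example shows that the curve can be marginally lower before the omitted death.

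**Conclusion.** The gap is real and follows from the text: criterion 3 has no route for an other-cause death before any post-baseline assessment, while Table 13 uses the FAS for two endpoints that count that death. The bias is confined to the supportive FAS curves and is upward from the time of the omitted death.

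Its size is modest: at most 3.3 points for two such deaths per 60, over the survival range considered. That figure rests on an assumed k, no censoring and N = 60. The documents do not show that any such death occurred.

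A reader might infer that the main efficacy result is in doubt. It is not. The ASaT curves, the primary ORR test, its alpha and its power do not use the FAS. For response rates the effect is one of denominators only, and in the example above it is 0.7 or 1.4 points.

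**What to change.** This is a cheap improvement. Either of two changes closes the gap for PFS and OS:

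- in Table 13, give ASaT as the only population for PFS and OS; or
- in 8.5.1, add death from any cause before the first post-baseline assessment as an entry route in criterion 3.

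If the FAS is kept for ORR and CRR, report by cohort how many treated subjects it excludes and why. The discontinuation reasons already planned in 8.6.3.1 cover only part of this. Do not relabel the set as response-evaluable, because criterion 3 deliberately admits unassessed subjects who stopped for progression or a drug-related AE.

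The cost is wording, with no new data. Section 8.0 lets changes to non-confirmatory analyses be documented in the supplemental SAP before final database lock. The first option gives up the supportive FAS tables for PFS and OS. The second keeps them, with slightly less favourable FAS estimates if such deaths occur.

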8.5.2 Safety Analysis Population

The All Subjects as Treated (ASaT) population will be used for the analysis of safety data in this study. The ASaT population consists of all enrolled subjects who received at least 1 dose of study treatment. At least one laboratory or vital sign measurement obtained subsequent to at least one dose of trial treatment is required for inclusion in the analysis of each specific parameter. To assess change from baseline, a baseline measurement is also required.

8.6 Statistical Methods

Unless specified otherwise, analyses will be conducted separately by Cohort.

Safety analyses are described in Section 8.6.2; efficacy results that will be considered to be statistically significant after consideration of the strategy for controlling the Type I error are described in Section 8.9, Multiplicity. Nominal p-values may be computed for other efficacy analyses as a measure of strength of association between the endpoint and the treatment effect rather than formal tests of hypotheses.

8.6.1 Statistical Methods for Efficacy Analyses

A summary of the primary analysis strategy for the primary and secondary efficacy endpoints is provided in [Table 13](#) below.

8.6.1.1 Overall Response Rate (ORR)

The primary efficacy endpoint for this study is the Overall Response Rate (ORR), defined as the proportion of subjects who have response (CR or PR) according to the IWG criteria, and will be analyzed separately by cohort. The primary analysis will be conducted for that cohort when the last subject in that cohort has reached the Week 12 response assessment or has discontinued study therapy.

The analysis will consist of the point estimate and 95% 2-sided exact confidence interval (CI) using the Clopper-Pearson method which will have at least 95% coverage of the true rate. An exact binomial test will be conducted for each cohort versus a fixed control rate for each cohort.

Secondary analyses for ORR will be performed based on investigator's (ie, study site) assessment and by central review based on the Lugano Classification (JCO, 2014).

Since an investigator may still continue to treat subjects with MK-3475 who have progressed according to central review or by site assessment, exploratory analyses (point estimate and 95% 2-sided exact confidence interval) will be conducted for ORR to consider these subjects who later achieve PR or CR post-progression as responders.

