7.1.2.6.3 Disease Assessment of Immunotherapeutic Agents

Immunotherapeutic agents such as pembrolizumab may produce antitumor effects by potentiating endogenous cancer-specific immune responses, which may be functionally anergic. The response patterns seen with such an approach may extend beyond the typical time course of responses seen with cytotoxic agents, and can manifest a clinical response after an initial increase in tumor burden or even the appearance of new lesions. Standard response assessment criteria may not provide a complete response assessment of immunotherapeutic agents such as pembrolizumab. Therefore in the setting where a subject assessment shows PD, study drug may be continued, at the discretion of the PI, until the next disease response assessment provided that the subjects' clinical condition is stable. However, imaging should occur at any time where there is clinical suspicion of progression.

NOTE: With next response assessment if the disease is clinically stable or clinically improved, an exception may be considered to continue treatment upon consultation with the Sponsor.

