As indicated in Section 8.6.1.1, the primary analysis of ORR will be conducted when the last treated subject has reached the Week 12 response assessment or has discontinued study therapy. At that time point, analyses of other efficacy endpoints in the table above (eg, DOR, CRR, PFS and OS) will also be conducted. An efficacy update for all endpoints in the table above will be conducted when the last treated subject has reached at least the Week 24 response assessment or has discontinued study therapy. An efficacy update will be conducted at one year after the last subject initiated treatment and then at 2 years after the last subject initiated treatment, which corresponds to the end of the protocol-specified treatment period. Subsequent yearly analyses will be conducted (ie, 3 years after the last subject initiated treatment, etc.) until the trial is complete, including follow-up information on subjects who enter the re-treatment period.

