8.9 Multiplicity

The false positive rate for testing the primary efficacy endpoint is controlled at 0.025 (1-sided) within each cohort. No additional multiplicity adjustment is required because each

cohort will be evaluated independently and only once, i.e. at the time of the primary analysis when all subjects in the cohort have reached the week 12 assessment or have discontinued study therapy.

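### The only formal ORR test is made at the last subject's Week 12 assessment, so late first responses in the last entrants are missed and the power in 8.8 is delivered only if 40% is the rate visible at that cut

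*Combined protocol and SAP*

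**What the plan says.** - **Endpoint (8.4.1):** the proportion of treated subjects with "complete remission (CR) or partial remission (PR) using IWG criteria (Cheson 2007) at any time during the study", by central review.
- **Time of the test (8.6.1.1):** "The primary analysis will be conducted for that cohort when the last subject in that cohort has reached the Week 12 response assessment". A subject who has already stopped treatment also satisfies the trigger.
- **Number of tests (8.9):** each "cohort will be evaluated independently and only once, i.e. at the time of the primary analysis".
- **Scans (7.1.2.6.4):** first at Week 12, then every 12 weeks. Treatment may run to 35 three-week cycles.
- **Later ORR analyses (text after Table 13, in 8.6.1.5):** "An efficacy update for all endpoints in the table above will be conducted when the last treated subject has reached at least the Week 24" assessment or has stopped therapy, then at one year, two years and yearly. None of these is a formal test.
- **Timing of response (7.1.2.6.3, also 4.2.3.2):** "The response patterns seen with such an approach may extend beyond the typical time course of responses seen with cytotoxic agents".
- **Power (8.8):** at least 93% for 40% against 20% with 60 subjects and one-sided alpha of 2.5%, or about 92% with the futility interim. The section does not say whether 40% is the any-time rate or the rate seen at the Week 12 cut.

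**The concern.** At the cut, early entrants have had two or more scans, but anyone who started in the last 12 weeks of accrual has had one scheduled scan. If such a subject first responds at Week 24, the response belongs to the endpoint as defined but is a non-response in the only test. What is tested therefore depends on how fast the cohort filled, and it can only lie at or below the any-time rate.

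A cohort whose any-time ORR is 40% could miss its threshold because its last entrants had not been followed long enough. The Week 24 update could then show the missing responses, but 8.9 gives that update no role in the hypothesis.

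**Working it through.** **1. Reproduce the stated power.** Inputs from 8.8 and 8.9: n = 60, null 0.20, alternative 0.40, one-sided alpha 0.025. The smallest count r with P(X ≥ r | 60, 0.20) ≤ 0.025 is 19:

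- P(X ≥ 18 | 0.20) = 0.0427 and P(X ≥ 19 | 0.20) = 0.0221.
- P(X ≥ 19 | 0.40) = 0.928. With the futility rule (stop at 6 or fewer of 30) it is 0.922.

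Both agree with 8.8 to rounding. The success threshold printed in 8.8, 16/60, does not fit: P(X ≥ 16 | 0.20) = 0.131. That is a separate inconsistency. The figures below use 19.

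**2. Share of a cohort on one scan (assumption).** No accrual period is stated. The nearest guide is the approximate 35-month trial duration less 35 × 3 = 105 weeks (24.1 months) of treatment, which leaves about 10.9 months. Under uniform accrual, share = 12 / accrual weeks:

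- 14 months (60.9 weeks): 0.197, about 12 of 60
- 11 months (47.8 weeks): 0.251, about 15 of 60
- 8 months (34.8 weeks): 0.345, about 21 of 60

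**3. Power at the Week 12 cut (assumption on late response).** Let q be the share of responders who first respond after Week 12, all of them at the second scan. With m one-scan subjects, the visible count is Bin(m, 0.40(1−q)) + Bin(60−m, 0.40), and power is P(count ≥ 19). For example, with m = 21 and q = 0.20 the visible ORR is (21 × 0.32 + 39 × 0.40)/60 = 0.372.

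| m | q = 0 | 5% | 10% | 20% | 30% |
|---|---|---|---|---|---|
| 12 | 0.9281 | 0.9192 | 0.9095 | 0.8875 | 0.8621 |
| 15 | 0.9281 | 0.9168 | 0.9042 | 0.8751 | 0.8402 |
| 21 | 0.9281 | 0.9119 | 0.8931 | 0.8472 | 0.7892 |

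**4. If late responses come later still.** Spread them equally over Weeks 24, 36 and 48, and credit each subject with every scan before the cut. With 11 months of accrual, the visible fraction of late responses at the Week 12 cut is (0.75 + 0.50 + 0.25)/3 = 0.50. At q = 0.20 the visible ORR is 0.40 × (1 − 0.20 × 0.50) = 0.36 and power is 79.7%. At q = 0.10 power is 87.5%.

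**5. Higher true ORR.** With m = 21, power is 96.1% at a true ORR of 45% and q = 20%, and 98.7% at 50% and q = 30%. At 53.3%, the Phase 1b Hodgkin figure in 4.2.1.2, it stays above 99% even with 28 one-scan subjects and q = 30%.

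**6. Does a second look at Week 24 cost alpha?** All subjects have been treated before the Week 12 trigger, so the ASaT denominator is fixed. With locked central reads, the number who have ever responded cannot fall. Rejecting at Week 12 or Week 24 with one critical count is therefore the same event as rejecting at Week 24. Simulation (q = 20%, 8 months) agrees. Under 20%, rejection is 0.010 at Week 12, 0.022 at Week 24 and 0.022 at either. Under 40%, it is 0.847, 0.928 and 0.928.

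**The case against.** The other side has several good points.

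- **Counting any-time response up to a data cut is ordinary practice.** A reader might infer that the definition and the timing contradict each other. They do not, but the rate that 8.8 refers to is left unclear. If 40% is meant as the rate at the cut, the stated power stands.
- **A reader might infer that 93% power holds only if nobody responds after Week 12.** That is too strong. Late responses in earlier entrants count if seen before the cut. A 5% late share at the second scan costs under 2 points.
- **The one-scan share and late-response share are assumptions.** The 35-month estimate cannot bound accrual, because yearly analyses run to three years and beyond after the last start and retreatment may add 17 cycles. Sections 2.1 and 8.0 also allow for markedly different enrolment rates between cohorts.
- **The remarks on late response are qualitative.** They partly describe response after apparent progression, which 8.6.1.1 handles in an exploratory analysis. The fix would not capture those responders.
- **Nothing here inflates type I error.** Missed responses only make rejection harder, and ORR with its exact interval is re-estimated at every update.
- **The outcome is known.** Section 4.3 reports cohort ORRs of 73.9%, 64.2% and 70.0%, so the documents do not support reading this as a threat to the trial's conclusion.

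These points limit the size of the problem. They do not remove the gap between the endpoint defined and the quantity tested, or the lack of any formal role for the planned Week 24 analysis.

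**Conclusion.** The concern holds as a conservative mismatch in the plan as designed. The single test at the Week 12 cut undercounts any-time response among the last entrants, and 8.8 delivers its power only if 40% is the rate visible then.

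If 40% is the any-time rate, and under the step 2 and 3 assumptions with 5-30% late responders, power is at most about 92%. It runs from about 92% down to about 79% when 25-35% of a cohort has one scan. Those figures treat anyone with two scans as fully ascertained, so later responses would widen the loss (step 4). There is no loss if no one responds late, and almost none if the true ORR is about 50% or more. This is a cheap improvement to the plan.

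**What to change.** Amend 8.6.1.1, 8.8 and 8.9, with matching text after Table 13:

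1. Keep the Week 12 analysis as the first point at which a cohort may declare success, and make the planned Week 24 analysis the final formal ORR test.
2. Use the same exact-test critical count at both: 19 for 60 treated subjects, recomputed if the cohort's ASaT size differs. Reconcile it with the 16/60 in 8.8.
3. Use the same ASaT denominator, and lock the central reads from the first cut. State that no alpha adjustment is needed because the count of subjects ever in response cannot fall.
4. State in 8.8 that 40% and the stated power refer to the Week 24 analysis, and show power over a range of late-response shares.

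**Cost.** No extra subjects, scans, analyses or alpha. A cohort that misses at Week 12 waits 12 weeks for its final conclusion. Section 8.0 requires a protocol amendment for a change to the primary method, and because 4.3 already reports cohort ORRs, a change made in this version must be labelled as made after results.

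**Limit.** Responses first seen after Week 24 in the last entrants are still missed. In the spread scenario of step 4 (11 months, q = 20%), the visible fraction of late responses at the Week 24 cut is (1 + 0.75 + 0.50)/3 = 0.75. The visible ORR is then 0.38 and power rises from 79.7% to 87.5%, not to 92.8%.
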